9.3. Clinical Laboratory Data

The hematology and clinical chemistry data will be summarized with descriptive statistics by treatment group and visit. Both observed values and changes from baseline will be summarized.

Shift tables will be presented for selected clinical laboratory variables based on the reference range-based categories of “Low,” “Normal,” or “High.” A clinical laboratory variable value will

be assigned to one of these three categories according to the reference ranges provided by the central clinical laboratory.

Two shift tables will be presented within the double-blind treatment period: shifts from baseline to the end of the titration and maintenance periods. Each shift table will have three rows and three columns, with rows reflecting the reference range category at baseline, and columns reflecting the reference range category at the specified postbaseline visit. A “Total” row and “Total” column will also be included. Subjects with a missing baseline value or who do not have postbaseline data will not be included in the tables for that variable. The number and percentage of subjects in each shift category will be displayed in the table; percentages will be based on the number of subjects included in the table.

Shift tables will be presented for the following clinical laboratory variables:

- aspartate aminotransferase (AST),
- alanine aminotransferase (ALT),
- gamma-glutamyl transferase (GGT),
- total bilirubin,
- creatine kinase,
- creatinine,
- blood urea nitrogen,
- white blood cell count,
- hemoglobin,
- platelet count,
- Free triiodothyronine (T3),
- Free thyroxine (FT4) and
- Thyroid stimulating hormone (TSH).

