#### 9.4.6. Clinical Laboratory Assessments

All clinical laboratory assessments will be performed by a central laboratory. In addition, a urine pregnancy test will be performed by the study site on Day 1 to confirm subject eligibility. The central laboratory will provide instructions and supplies to the study staff before study initiation and instructions will be included in a laboratory manual. The laboratory test battery will include routine and screening laboratory tests.

The following clinical safety laboratory assays will be performed:

Hematology: complete blood count including white blood cell (WBC) count with differential, red blood cell (RBC) count, hemoglobin, hematocrit, and platelet count, mean corpuscular hemoglobin (MCH), mean corpuscular hemoglobin concentration (MCHC), mean corpuscular volume (MCV), red cell distribution width (RDW), mean platelet volume (MPV).

Neurocrine Biosciences, Inc., Study No. NBI-827104-CSWS2010 Clinical Protocol Amendment 3.0

Clinical Chemistry: sodium, potassium, calcium, magnesium, phosphorus, chloride, blood urea nitrogen, bicarbonate, creatinine, uric acid, albumin, alkaline phosphatase, lactate dehydrogenase, AST, ALT, GGT, creatine kinase, total bilirubin, total cholesterol, triglycerides, total protein, glucose, TSH, T3 (free fraction), and T4 (free fraction).

Urinalysis: specific gravity, nitrite, ketones, protein, urobilinogen, glucose, bilirubin, leukocyte esterase, occult blood, and pH; microscopic examination of sediment will be performed only if the results of the urinalysis dipstick evaluation are positive for nitrite, protein, leukocyte esterase, or blood. Urine samples may be considered optional if the subject is unable to provide urine (eg, participant is in a diaper).

The following additional laboratory tests will be performed:

Serology: Blood will be collected for HIV-Ab, HBsAg, and HCV-Ab and reflex nucleic acid amplification testing (if applicable) at screening.

Drug screen: Blood will be collected at screening for a cannabinoid drug testing. A urine cannabinoid drug test may be performed if blood test results are not available prior to randomization at Day 1.

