### 13. STATISTICAL AND ANALYTICAL PLAN

#### 13.1. Overview

The analysis plan provided in this protocol represents a brief description of the planned analyses. The comprehensive statistical analysis plan (SAP) will be generated prior to final study database lock. The SAP may include a number of additional analyses and data summaries not described in this protocol.

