# 13.11. Safety Data

[figure not shown]
Safety analyses will be performed using the Safety set.

AEs will be summarized (frequency counts and percentages) by system organ class and/or preferred term, and maximum intensity.

Descriptive summary statistics of the observed values and changes from baseline to each scheduled visit in clinical laboratory parameters will be provided. The number (%) of subjects with marked laboratory abnormalities will be tabulated.

Observed values and changes from baseline to each scheduled visit in vital signs (SBP and DBP, pulse rate), ECG parameters (QTcF, HR, PR interval, QRS duration), and C-SSRS will be summarized. The number (%) of subjects with marked ECG abnormalities will be tabulated.

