4.3.4. Early Termination Data

Early termination (ET) data collected at postbaseline unscheduled visits will be mapped to the next subsequent visit where the applicable assessment would have been performed for the purpose of statistical summarization. ET data collected at a scheduled visit per the protocol schedule of assessments will be mapped to that scheduled visit for applicable data summaries.

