9. SAFETY

The safety objective of the study is to characterize the safety profile of NBI-827104 as measured by TEAEs and SAEs, clinical laboratory tests, vital signs, ECG, and the C-SSRS. All outputs for safety endpoints will be based on the safety analysis set. The analysis of the safety data will be based on descriptive statistics and presented by treatment group according to the study visit unless otherwise noted. Data from the neurological and ophthalmic examinations will not be summarized because any abnormal results were assessed for AE reporting by the investigator and will be captured in the AE summaries. Safety data will not be subject to any imputation and will be summarized on an observed case basis. No formal hypothesis-testing analysis of safety data will be performed.

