9.5. Electrocardiogram

The triplicate ECG parameter values recorded at each timepoint for heart rate, PR interval, QRS duration, QT interval, and QTcF (corrected QT interval using Fridericia's formula) interval will be averaged (and rounded to the nearest whole number) for each subject and timepoint for the purpose of statistical summarization. Additionally, for the triplicate investigator overall categorical assessment (ie, Normal, Abnormal not Clinically Significant, or Abnormal Clinically Significant) at each timepoint, the outcome representing the greatest degree of abnormality will be selected for summarization.

Descriptive statistics for the observed values and changes from baseline will be presented for each of the ECG parameters by timepoint and treatment group.

Frequency tables (number and percentage of subjects) will be presented for the overall categorical assessment at each timepoint.

Two additional categorical summaries (frequency tables displaying number and percentage of subjects) will be presented for the QTcF interval by treatment group. For the first summary, the observed QTcF values at each timepoint will be classified as follows:

- Greater than 450 msec
- Greater than 480 msec
- Greater than 500 msec

For the second categorical summary, the changes from baseline to each subsequent timepoint will be classified as follows:

- Increase greater than 30 msec
- Increase greater than 60 msec

The same categorical summaries will be presented in frequency tables for values at any postdose timepoint (including unscheduled assessments) meeting the aforementioned criteria.

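### SAP 9.3 as published omits the count of subjects with marked laboratory abnormalities that Protocol 13.11 commits to; separately, SAP 9.4 and Protocol 9.4.2 disagree on orthostatic posture

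*SAP*

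**What the plan says.** Protocol 13.11 lists the safety summaries. For laboratory data it promises descriptive statistics of observed values and changes at scheduled visits, and then: "The number (%) of subjects with marked laboratory abnormalities will be tabulated". It makes a parallel promise for marked ECG abnormalities. On how the two documents relate, Protocol 13.1 says: "The SAP may include a number of additional analyses and data summaries not described in this protocol". That sentence allows additions; it does not mention leaving out a summary that the protocol states.

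SAP 9.3, which shows no redaction, plans two kinds of laboratory output:
- descriptive statistics for hematology and chemistry by arm and visit, for observed values and changes from baseline;
- shift tables for 13 selected variables, using the categories Low, Normal and High. On timing: "Two shift tables will be presented within the double-blind treatment period: shifts from baseline to the end of the titration and maintenance periods". On content: "The number and percentage of subjects in each shift category will be displayed in the table".

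SAP 9 says that safety results are "presented by treatment group according to the study visit unless otherwise noted".

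On vital signs, SAP 9.4 derives orthostatic blood pressure and heart rate as the standing value minus the sitting value. Protocol 9.4.2 has blood pressure and pulse taken after at least 5 minutes supine and again after about 2 minutes standing.

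**The concern.** A safety count that the protocol promises has no counterpart in the section of the SAP that should carry it. Safety and tolerability in children aged 4 to 12 is the secondary objective, and a count of children per arm with a marked value is a direct way to report laboratory safety.

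Timing matters too. The visible protocol does not define *marked*. SAP section 1 requires decisions on the final analysis before database lock and unblinding, and SAP 4.1 treats anything defined after lock as post hoc. If the gap stays, the promised summary will either be missing or rest on criteria chosen after lock.

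The posture point is smaller. The SAP formula needs a sitting reading, and the visible protocol text does not collect one.

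**Working it through.** The plan gives no figure to reproduce here, and no power or type I error calculation is involved. The check sets the commitment beside the planned outputs and asks whether the outputs contain the count.

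**1. What is promised.** Protocol 13.11 promises a number and percentage of subjects with a marked laboratory abnormality. It gives no threshold, list of analytes or time window.

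**2. What SAP 9.3 contains.** It contains no table under that name, no multiple of the upper limit of normal (ULN), no grade and no rule for a subject's worst value.

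**3. Whether the count follows from what is planned.**
- *Descriptive statistics.* SAP 4.1 defines these as n, mean, median, SD or SE, minimum and maximum. If the maximum at a visit is below a limit, no child exceeded it at that visit. If the maximum is above the limit, at least one child did, but the maximum does not say how many.
- *Shift tables.* These do count children by arm, but against the reference range. High covers every value above the range, so a value just above ULN and one at 2.5 times ULN (the ALT/AST level that Protocol 9.8.1 gives as an example of clinical significance) fall in the same cell. Exclusion 13 bars AST, ALT and GGT only above 2 times ULN. Subject to exclusions 9 and 12, a child can therefore enter as High and remain High to High however far the value rises. The tables cover 13 variables at two timepoints.
- *Unscheduled values.* SAP 4.3.4 has early-termination data from unscheduled visits "mapped to the next subsequent visit where the applicable assessment would have been performed". SAP 9.1 assigns dose reductions at unscheduled visits to the next scheduled visit. No visible rule covers other unscheduled laboratory values.

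Neither output provides the promised count.

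**4. The parallel ECG commitment.** SAP 9.5 sets QTcF cut-offs by visit and adds: "The same categorical summaries will be presented in frequency tables for values at any postdose timepoint (including unscheduled assessments) meeting the aforementioned criteria". SAP 9.6 likewise uses the maximum suicidal ideation score over scheduled and unscheduled visits. So the SAP gives the ECG promise explicit thresholds and leaves the laboratory promise without any.

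**5. Scale of the missing count.** With 24 subjects randomized 2:1, the arms are 24 × 2/3 = 16 and 24 × 1/3 = 8. One child is 1/16 = 6.3% of the active arm or 1/8 = 12.5% of the placebo arm. This shows how coarse the table would be; it does not measure an error.

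**6. Posture.** The SAP formula is standing minus sitting. The visible protocol readings are supine and standing. On that text, the sitting value in the formula has no source.

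**The case against.** The case against making much of this is substantial.

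- *The data are not unreported.* Every hematology and chemistry analyte has by-visit minimum and maximum values, observed and as change. A child with an extreme rise who stays High to High would set the maximum if it were the most extreme in the arm. This partly offsets the lack of grading.
- *Other cover exists.* Adverse events include those found through laboratory results. SAP 9.2 counts each child with a treatment-emergent event without restriction to a visit, and the DMC reviews safety throughout. This is real cover, but adverse event recording depends on the investigator's judgement and is not the promised count.
- *The text may be hidden.* SAP section 11 is redacted in both title and content and could hold criteria. SAP 9.3 does not refer to it, but absence cannot be proved.

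Two stronger readings are tempting, and the documents do not support either.

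First, a reader might infer that the protocol promised a count at any time or by worst value. It did not: the sentence gives no time window, and the one before it refers to scheduled visits. A by-visit table of marked values would meet its wording.

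Second, a reader might infer that the shift tables fall short of a requirement. Protocol 9.4.6 names 25 chemistry and 10 hematology analytes (the white-cell differential counted once with the white-cell count), 35 in all, so 35 − 13 = 22 have no shift table. But the protocol section promises no shift tables, SAP 9.3 limits them to selected variables, and nothing says that the marked count must cover all 35. The figure of 22 describes the tables; it is not a breach.

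On posture, the protocol text is partly broken in the public copy and the schedule of assessments is not shown, so a sitting reading may be specified where it cannot be seen.

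**Conclusion.** The gap holds on the visible text: a tabulation stated in Protocol 13.11 is not carried into SAP 9.3, and the planned laboratory outputs do not supply it. It is minor. It affects descriptive safety reporting only; SAP 9 plans no formal test of safety data, and no efficacy result changes. Its size is one missing table and one missing definition. The conclusion assumes that the redacted section 11 does not already contain them.

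The posture mismatch is a separate, editorial contradiction between a stated formula and the readings visibly collected. The documents do not show which posture is intended.

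**What to change.** In SAP 9.3, add one descriptive table by arm giving the number and percentage of subjects with a marked laboratory abnormality. State the criteria and the analytes they cover before unblinding, and say that they serve reporting only. Preferably, count each subject's worst post-baseline value, including unscheduled visits, on the model of the QTcF table in SAP 9.5. That choice is a recommended improvement beyond the protocol's wording. If section 11 already holds the criteria and table, refer to it from 9.3 instead.

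Reconcile SAP 9.4 with Protocol 9.4.2 so that the orthostatic formula uses the posture actually recorded.

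The cost is one extra table from central laboratory data already collected, agreement on the criteria, and one wording change. Study conduct and hypothesis tests are unaffected.

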### 9.8. Discontinuation of Study Treatment and Subject Withdrawal

Subjects/caregivers can discontinue study treatment or withdraw their consent to participate in the study at any time. The investigator must discontinue study treatment dosing or withdraw any subject from the study if a subject/caregiver requests study treatment dosing to be discontinued or to be withdrawn from the study, respectively. All subjects prematurely discontinuing study treatment dosing should continue study participation to be followed for safety and efficacy outcomes.

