### 9.8.1. Discontinuation of Study Treatment Dosing

If a subject prematurely discontinues study treatment dosing, the investigator will record the reason for discontinuation on the relevant eCRF. Such subjects will not be automatically withdrawn from the study and should continue participation in the study. The investigator, subject's parent/legal guardian, and subject should discuss a plan for continued participation. Data for any outcome measures, particularly the primary endpoint, as well as safety follow-up, are important to collect. For any subsequent study visits after study treatment is prematurely discontinued, subjects will not be required to undergo PK sampling. Additional study visits and assessments for participants who discontinue study treatment but agree to remain in the study may be conducted remotely. If medically indicated, treatment with medication listed under Section 9.7.1 is no longer prohibited after study treatment discontinuation.

Reasons for discontinuation from study treatment include but are not limited to:

- Withdrawal by subject
- Death
- Lost to follow-up
- Site termination by the Sponsor
- Study termination by the Sponsor
- AE
- Pregnancy
- Lack of efficacy

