#### Protocol deviation

The investigator must discontinue study treatment dosing if the subject experiences any of the following:

- If the type, frequency, or severity of any AE becomes unacceptable/intolerable, despite attempts to decrease the dose.
- If the subject is unable to tolerate the lowest allowable study dose (ie, dose level 1).
- QTcF value >500 msec (cardiologist verified) on any ECG tracing.
- If the subject exhibits suicidal behavior, or suicidal ideation of type 4 (active suicidal ideation with some intent to act, without specific plan) or type 5 (active suicidal ideation with specific plan and intent) based on the C-SSRS, or in the opinion of the investigator.
- Subject is confirmed to be pregnant.
- Subject has any clinically significant treatment-emergent ophthalmic finding.
- Subject has any clinically significant treatment-emergent thyroid function test abnormality (TSH, T3 [free fraction], and T4 [free fraction]).

The investigator or the Sponsor may discontinue study treatment dosing for other reasons including those described below.

- Subject develops a clinically significant laboratory (eg, ALT or AST ≥2.5 times ULN) or ECG abnormality.
- Subject requires a medication that is prohibited by the protocol.

It is crucial to obtain follow-up data for any subject who discontinues study treatment dosing because of an AE, abnormal laboratory test, vital sign measurement, physical and neurological examination, ECG finding, or ophthalmic evaluation. In any case, every effort must be made to undertake safety follow-up procedures.

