All available study data will be included in relevant data displays, including data for subjects with incomplete or missing values. Replacement of missing data values with imputed values will generally not be performed unless specified otherwise in relevant endpoint subsections.

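### SAP 9.3 shows laboratory shifts at two visits only and mixes on-drug with off-drug samples, so the laboratory tables can understate thyroid shifts on NBI-827104

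*SAP*

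**What the plan says.** Protocol 9.8.1 lists findings under a compulsory instruction: "The investigator must discontinue study treatment dosing if the subject experiences any of the following". One item reads: "Subject has any clinically significant treatment-emergent thyroid function test abnormality (TSH, T3 [free fraction], and T4 [free fraction". Protocol 9.8 then asks that such children stay in the study: "All subjects prematurely discontinuing study treatment dosing should continue study participation to be followed for safety and efficacy outcomes". Protocol 9.8.1 adds a practical limit: "Additional study visits and assessments for participants who discontinue study treatment but agree to remain in the study may be conducted remotely".

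SAP 4.2 analyses the safety set by treatment received, so a child dosed with NBI-827104 stays in that arm after stopping. SAP 4.1 sets the general data rule: "All available study data will be included in relevant data displays, including data for subjects with incomplete or missing values". SAP 9 uses observed cases without imputation, with results "presented by treatment group according to the study visit unless otherwise noted".

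SAP 9.3 summarises haematology and chemistry by arm and visit. For 13 variables, including TSH, free T3 and free T4, it specifies: "Two shift tables will be presented within the double-blind treatment period: shifts from baseline to the end of the titration and maintenance periods". The column category is the one at the named visit. Nothing readable in SAP 4, 9 or 9.3 sets an on-treatment window for laboratory samples or asks for a worst postbaseline value.

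Two neighbouring sections do look across all visits. SAP 9.5 repeats the QTcF categories for "values at any postdose timepoint (including unscheduled assessments) meeting the aforementioned criteria". SAP 9.6 builds the C-SSRS shift table on the maximum score over all scheduled and unscheduled postbaseline assessments.

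**The concern.** The protocol treats thyroid function as a named risk with its own compulsory stop. That stop acts on the same laboratory result that the shift tables are meant to display. A child with a significant TSH, free T3 or free T4 change comes off drug, may recover, and is then tabulated at end of maintenance on a sample that no longer reflects exposure. If the abnormal value was taken at neither of the two shift visits, no shift table records it.

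The direction is toward showing no effect. With 16 treated children, a reader of the thyroid shift table could see no shifts when some occurred on drug. Out-of-range values that are not reported as adverse events have no other patient-level display specified in SAP 9.3. The pooling of on-drug and off-drug samples also affects the by-visit means for the arm.

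**Working it through.** The documents give no rate of thyroid stops and no figure of their own on this point to reproduce. The check follows one child through the written rules and then sizes the effect.

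**Tracing one child.** Assume a child on NBI-827104 with an in-range baseline, and a thyroid value on drug that is outside the central laboratory's range and leads to the compulsory stop.

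| Where the abnormal value is found | Where SAP 9.3 shows it |
|---|---|
| End-of-titration visit | In the end-of-titration shift table |
| Scheduled visit between the two shift visits | In neither shift table; it enters that visit's mean, minimum and maximum (SAP 4.1 defines the statistics) |
| Unscheduled sample | In neither shift table; SAP 9.3 gives it no by-visit row |

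In the last two cases, the end-of-maintenance table then depends on the later sample:

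- sampled, back in range off drug: Normal to Normal under NBI-827104;
- sampled, still out of range: shown as a shift;
- not sampled: absent from that table.

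**Arm size.** Inputs are from SAP 3.1 and Protocol 8.4. The sentinel cohort has 4 active and 2 placebo. The main cohort has 18 at 2:1, so 18 × 2/3 = 12 active and 6 placebo. Active: 4 + 12 = 16. Placebo: 2 + 6 = 8. Total: 24, which agrees with the planned sample size.

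**Effect on the table.** Let k be the number of NBI-827104 children whose abnormality falls outside the two shift visits and who have recovered by end of maintenance. The documents do not give k; 1 to 3 is an assumed range. The other children are taken to have no shift.

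| k | Planned table, all sampled | Planned table, the k children not sampled | Worst postbaseline table, k/16 |
|---|---|---|---|
| 1 | 0/16 | 0/15 | 6.3% |
| 2 | 0/16 | 0/14 | 12.5% |
| 3 | 0/16 | 0/13 | 18.8% |

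Each child moves the percentage by 1/16 = 6.25, or 6.3 points.

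**Chance that the situation arises.** If the rate of thyroid stops is p, the chance of at least one among 16 is 1 − (1 − p)^16:

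- p = 5%: 1 − 0.440 = 56%
- p = 10%: 1 − 0.185 = 81%
- p = 20%: 1 − 0.028 = 97%

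These rates are assumptions. The result is the chance of at least one thyroid stop. The chance of a stop that is also missed by both shift tables is no larger, and smaller if some stops follow an abnormal end-of-titration value.

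**The case against.** The strongest reply is that the event is not lost. A thyroid abnormality that stops dosing should be recorded as an adverse event. SAP 9.2 then puts it in the table of events leading to drug discontinuation and in a listing with arm, dose and study day. In a trial of this size that listing is informative, and a later normal value beside it reads as recovery. This stands, and it limits the point to the laboratory tables.

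A reader might infer that every child stopped under the thyroid rule will be reported as Normal. The documents do not support that. Visits after stopping may be remote, so there may be no sample; recovery may be incomplete; and an abnormal end-of-titration value is still tabulated. A scheduled intermediate value can show in that visit's minimum or maximum. The schedule of assessments is not shown, so it cannot be said how often an abnormal value would fall outside the two shift visits.

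A reader might also infer that liver enzymes behave the same way. Protocol 9.8.1 places ALT and AST among the reasons for which dosing may be stopped, not among the compulsory ones.

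The QTcF and C-SSRS rules might be read as precedents for excluding off-drug data. They are not: both take any postdose or postbaseline assessment. They are precedents for a worst-value table only.

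On the other side, the words about the double-blind treatment period in SAP 9.3 might be read as an on-drug restriction. They name study periods, not an individual child's exposure.

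**Conclusion.** The point holds as a gap in the laboratory displays. SAP 9.3 can understate on-drug thyroid shifts, because it looks at two visits only and does not separate samples by whether the child was still on drug. Each affected child is 6.3 percentage points of a 16-child arm. The number affected is an assumption, and so are an in-range baseline and recovery or no sample by end of maintenance.

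This is a cheap improvement, not a finding that the safety event would be hidden. Three stronger inferences do not follow:

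- The 21 and 18 evaluable children in SAP 3.4 do not indicate how many would contribute off-drug blood samples. Those counts concern the EEG endpoint, and a child without an overnight EEG may have no blood sample either.
- The case does not carry over to the by-visit vital-sign and ECG means. No comparable bias is shown there, and QTcF already has an any-time table.
- It does not follow that samples after the last dose should be removed. A sample drawn just after stopping may still reflect the drug, and SAP 9.2 itself tabulates events up to 14 days after the last dose.

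**What to change.** In SAP 9.3, for the 13 listed variables, add a shift from baseline to the worst postbaseline value, once toward Low and once toward High. Use every scheduled and unscheduled sample after the first dose. This follows the approach already in SAP 9.5 for QTcF and SAP 9.6 for C-SSRS.

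Keep the by-visit summaries and both existing shift tables. Flag samples taken after the child's last dose date and show them in a separate row or listing. Keep samples drawn shortly after the last dose in the worst-value table, with the flag visible.

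The cost is one more table and one date flag programmed from dose and sample dates, plus a few lines of SAP text. The number of children in the on-drug rows will be smaller at late visits. No clinical rule changes.
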